# **12 Ethical Considerations**

This protocol and any amendments will be submitted to a properly constituted independent Ethics Committee (EC) or Institutional Review Board (IRB), in agreement with local legal prescriptions, for formal approval of the study conduct. The decision of the EC/IRB concerning the conduct of the study will be made in writing to the investigator and a copy of this decision will be provided to the sponsor before commencement of this study. The investigator should provide a list of EC/IRB members and their affiliate to the sponsor.

All subjects for this study will be provided a consent form describing this study and providing sufficient information for subjects to make an informed decision about their participation in this study. See the ARROW application for a copy of the consent form. This consent form will be submitted with the protocol for review and approval by the EC/IRB for the study. The formal consent of a subject, using the EC/IRB-approved consent form, must be obtained before that subject undergoes any study procedure. The consent

Version #: 1.0

[name]

form must be signed by the subject or legally acceptable surrogate, and the investigator-designated research professional obtaining the consent.

# **13 Study Finances**

# 13.1 Funding Source

This study is funded by a seed grant from the University of Wisconsin Global Health Institute.

#### 13.2 Conflict of Interest

Any investigator who has a conflict of interest with this study (patent ownership, royalties, or financial gain greater than the minimum allowable by their institution, etc.) must have the conflict reviewed by a properly constituted Conflict of Interest Committee with a Committee-sanctioned conflict management plan that has been reviewed and approved by the study sponsor prior to participation in this study. All UW investigators will follow the UW conflict of interest policy.

#### **14 Publication Plan**

Neither the complete nor any part of the results of the study carried out under this protocol will be published or passed on to any third party without the consent of the study sponsor. Any investigator involved with this study is obligated to provide the sponsor with complete test results and all data derived from the study.

# Appendices

## Appendix 1 - Screening Questions, Demographic Information, and Past Medical History

# Screening Questions for Program Participation

- "Have you been diagnosed with diabetes "1 (Y/N)
  - If NO, application comes to a hard stop and the patient is advised that this program is only for patients who have been diagnosed with diabetes
  - If YES, "Have you been told that your diabetes is type 1 diabetes " (Y/N)
    - If YES, application comest to a hard stop and the patient is advised that the program is only for patients with type 2 diabetes. Patient is referred to San Lucas Mission Hospital for further cares
    - If NO, application proceeds to the next question
  - "Are you 18 years of age or older " (Y/N)
    - $\circ$   $\;$  If YES, application continues to the next question
    - If NO, application comes to a hard stop and the patient is advised that the program is not for patients younger than age 18. Patient is referred to San Lucas Mission Hospital for further cares
- "Are you taking insulin for your diabetes " (Y/N)
  - If NO, application continues to the next question
  - If YES, application comes to a hard stop and the patient is advised that the program is not for patients who require insulin to control their diabetes. Patient is referred to San Lucas Mission Hospital for further cares.
  - Application prompts promoter, "What is the patient's sex " (M/F)
- If M, application proceeds to next section
  - If F, application prompts promoter to ask patient "Are you currently pregnant" (Y/N/UNSURE)
    - "Have you gone through menopause " (Y/N)
      - If YES, application continues to enrollment procedures
      - If NO, application continues to next question
      - "Have you had a tubal ligation " (Y/N)
        - If YES, application continues to enrollment procedures
        - If NO, application continues to next question
      - "Are you currently pregnant " (Y/N/UNSURE)
        - If NO, application proceeds to next section
          If YES, application comes to a hard stop and the patient is advised that the program is not designed for pregnant women with diabetes. Patient is referred to San Lucas Mission Hospital for further cares.
        - If UNSURE, urine pregnancy test is conducted
          - If NEGATIVE, application proceeds to next section
          - If POSITIVE, application comes to a hard stop and the patient is advised that the program is not designed for pregnant women with diabetes. Patient is referred to San Lucas Mission Hospital for further cares.

<sup>1 Unless otherwise specified, questions or other elements in quotation marks are addressed to the patient

<sup>2 Promoter=Community Health Worker (CHW)

<sup>3 Female patients will be assessed for possible pregnancy in this way at monthly visits as well

[name]

#### Basic Demographic Information

- Application prompts promoter to enter name, sex, and community (from pull down menu prepopulated with all possible communities)
- Application asks the promoter: "Is the exact date of birth known " (Y/N)
  - If YES, application prompts promoter to enter DOB and calculates age from this
  - If NO, application prompts patient to enter age in years
- Application asks promoter: "What language does the patient prefer to communicate in ". Possible responses are Spanish or Kaqchikel and are selected from a drop down menu

#### Past Medical History

- "How many years have you had diabetes " (accepts integers 0-100)
- "Where were you diagnosed " (Pull down menu with common sites/means of diabetes diagnosis: San Lucas Hospital, government health center, IGSS, health promoter, visit from foreign doctor, private doctor or nurse, other)
- Application asks promoter: "Does the patient have IGSS " (Y/N)
- "Do you smoke " (Y/N)
- "Do you take natural medicines for diabetes" (Y/N)
- "Have you had any of the following conditions or illnesses " (application allows for selection of any of the below options):
  - Cancer
  - Emphysema/COPD
  - Chronic kidney disease
  - Heart attack
  - Stroke
  - High blood pressure (hypertension)
  - None of these (can't be selected if other option is selected)
- If option selected for "stroke", application prompts promoter to ask: "Was the stroke caused by bleeding in the brain " (Y/N)

## Determining if contraindications or need for precautions are present

- "Have you ever had an allergy to aspirin causing difficulty breathing, low blood pressure, or other severe illness " (Y/N)
  - If YES, aspirin not prescribed
  - If NO, continue to next question
  - "Have you recently had blood in your stool or black and tarry stools " (Y/N)
    - o If YES, aspirin not prescribed, referred to medical director for further recently
    - If NO, continue to next question
  - "Have you ever had a stomach ulcer " (Y/N)
    - $\circ~$  If YES, aspirin prescribed and patient recommended to take omeprazole or ranitidine while taking aspirin
    - If NO, continue to next question
  - "Do you have frequent pain in the upper part of your belly or heartburn " (Y/N)
    - If YES, aspirin prescribed and patient recommended to take omeprazole or ranitidine while taking aspirin
    - If NO, aspirin prescribed
  - Blood pressure measured later in the visit
    - If BP<160/100 mmHg, aspirin prescribed

      - $\circ~$  BP ≥160/100 mmHg  $\rightarrow$  referred to medical director for BP management, aspirin not prescribed until BP better-controlled

## Appendix 3 - Medication History, Side Effects, and Adherence

#### Medication History

- "Are you taking Metformin " (Y/N)
  - If NO, application skips to next question
  - If YES, "Are you only taking 1 pill size of Metformin " (Y/N)
    - If YES, "How many milligrams are the Metformin pills " (can select 500 mg, 850 mg, or 1000 mg, which are commonly available sizes in the area) and "How many Metformin pills do you take daily " (select from ½, 1, 2, 3, and 4)
    - If NO, "How many milligrams of Metformin do you take in total per day " (numeric entry box)
- "Are you taking Glibenclamide" (Y/N)
  - If NO, application skips to next question
  - If YES, "Are you only taking 1 pill size of Glibenclamide " (Y/N)
    - If YES, "How many milligrams are the Glibenclamide pills " (select 5 mg or 10 mg, the commonly available sizes in the area) and "How many Glibenclamide pills do you take daily " (select ½, 1, 2, 3, or 4)

<sup>7 These considerations are based on the Aspirin Guide clinical decision support tool, which provides guidance on the use of ASA in primary and secondary ASCVD prevention and is in turn based on guidance from the USPSTF

#### [name]

- If NO, "How many milligrams of Glibenclamide do you take in total per day " (numeric entry box)
- "Are you taking any other medication for diabetes prescribed by a doctor " (Y/N)
- If NO, application skips to next question
  - If YES, application prompts promoter to enter medication name (free text), milligram strength of pills (numeric entry), and number of pills per day (½, 1, 2, 3, or 4)
- If patient not currently taking any medication, application prompts promoter to ask, "Have you previously taken medication for diabetes " (Y/N)
  - If YES, questions regarding medication side effects appear (These also appear if patient is taking any of the aforementioned medications)
  - If NO, application skips to the next section
  - "Are you currently taking medication for high blood pressure " (Y/N)
  - If YES
    - Application prompts promoter to collect information about name of medication (free text) and dosage (numeric entry)
    - Renal function testing will be recommended for this patient
    - Application skips to the next section
    - If NO, application skips to the next section

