### 2.3 Study Agent

In this study, we will be using a smartphone application that we developed to guide CHWs through the clinical assessment of patients with diabetes including collection of demographic data and past medical history, assessment of medication history, adherence, and adverse effects, measurement of glycemic control, screening for complications, medication administration and titration, and patient counseling. The application uses the CommCare platform by Dimagi and will be run on password-protected and encrypted Android smartphones. This application is based on web forms, which allow for skip logic questions and algorithmic processing of data. The application can be used offline. When internet access is available, collected data is uploaded to a secure server. The specific protocols and algorithms programmed into this application are described in further detail in the relevant sections of this protocol and its appendices.

We will use the following medications in our study (all FDA approved and being used for approved indications):

- Metformin HCI regular-release tablets 850 mg
  - Description: Oral biguanide antidiabetic medication. First line medication for type 2 diabetes and used as monotherapy or in combination with other medications. Low risk of lactic acidosis

Version #: 1.0

Deleted: consists of Enketo

Deleted: utilize Excel-based programing to

Deleted: These forms run in a smartphone browser and

**Deleted:** In our case, we are using password-protected Android smartphones with the Google Chrome mobile browser.

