# 7 Study Procedures

# 7.1LABS

All patients will have POC HbA1c testing performed at baseline and every 3 months. The ADA does recommend individualization of A1c testing, advising quarterly checks in patients not meeting glycemic goals and at least twice yearly in those meeting treatment goals. While we do intend to implement individualized testing in the diabetes program after the study period, testing will be every 3 months for all patients during the study period to allow for more uniform evaluation of program efficacy at the predetermined times of endpoint analysis (6 and 12 months for primary endpoints).

A1c testing will be performed with A1CNow®+ (PTS Diagnostics) POC capillary blood analyzers. This analyzer has been granted a CLIA waiver and has been certified by the National Glycohemoglobin Standardization Program (NGSP).

Capillary blood glucose measurements will be conducted at baseline and monthly using the Bayer Contour® POC system. This is also CLIA-waived and has been validated in comparisons with plasma/serum glucose analyzers.

Both aforementioned POC testing systems are designed to be used by laypeople and patients without medical training, making them very appropriate for use by frontline health workers, as in our study.

Testing of serum creatinine will be checked at baseline for all patients with prior history of chronic kidney disease prior to administration of metformin or glibenclamide. Baseline creatinine will also be strongly recommended for patients with hypertension (defined as either taking antihypertensives or baseline BP  $\geq$ 140/90) and/or duration since diagnosis of diabetes of 10 years or more. Serum creatinine will be checked at SLMH and reviewed by the medical director, who will then determine patient eligibility for metformin and/or glibenclamide therapy based on calculated eGFR.

Ideally, serum creatinine would be tested in all patients at baseline and prior to administration of metformin and glibenclamide. However, this is not performed routinely for diabetic patients in the San Lucas area due to the expense and availability of travel. Requiring testing for all patients prior to administration would likely severely restrict participation as it is likely many patients would not travel to San Lucas to have necessary testing done and subsequently be lost to follow up. For this reason, we have adopted a risk-factor based targeted testing strategy for checking renal function.

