### Enrollment Visit

0

Patients will be screened for study eligibility on the same day of potential enrollment. If they are eligible, informed consent will be obtained and the CHW will proceed with enrollment and initial treatment of the patient with the guidance of the enrollment module of the smartphone application. The enrollment visit will consist of the following elements:

- Screening questions (Appendix 1) Determine if patient is eligible to participate in the study. Done with verbal consent. If eligible, written and verbal consent obtained for full study participation and CHW proceeds to the next step.
- Collection of demographic information and relevant past medical history (Appendix 1) This information facilitates the creation of a patient database and clinical registry, determines the patient's glycemic goal and if they need renal function testing prior to initiation of medications, and informs a decision about chronic aspirin therapy for secondary ASCVD prevention (Appendix 2). Glycemic goals are generally consistent with ADA guidelines and are determined as follows:
  - Patients <65 years old with <2 comorbidities (CAD, CVD, COPD, CKD, cancer)
    - A1c goal ≤7%
    - FBG 80-130 mg/dL
    - PPBG <180 mg/dL

    - Patients ≥65 years old or <65 years old and with ≥2 comorbidities (as listed above)
      - A1c goal ≤8%
      - FBG 90-150
      - PPBG <200 mg/dL

- Medication history, adherence and side effects (Appendix 3) This information factors into the confirmation of diabetes with A1c testing (for example, if a patient is not taking any medications and their A1c is 5.2, they may not have diabetes) and provides information for the application to determine starting medication for each patient. Information about whether a patient is taking medication for hypertension will also factor into whether renal function testing is recommended prior to initiating medication treatment.

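### As printed, Appendix 3 routes a never-treated patient past the antihypertensive question, which conflicts with the renal-testing trigger in Sections 7.1 and 7.4.1

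*Combined protocol and SAP*

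**What the plan says.** Appendix 3, Medication History, lists items on metformin, glibenclamide and other prescribed diabetes drugs. For each, a negative answer reads "If NO, application skips to next question". A patient on none of these is then asked about past diabetes medication. On YES, "questions regarding medication side effects appear (These also appear if patient is taking any of the aforementioned medications". On NO, "If NO, application skips to the next section".

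The next printed item, under the same heading, is "Are you currently taking medication for high blood pressure". Its YES branch includes "Renal function testing will be recommended for this patient", and both its YES and NO branches end by moving to the next section.

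Section 7.1 makes baseline creatinine mandatory for patients with known kidney disease. It is "strongly recommended for patients with hypertension (defined as either taking antihypertensives or baseline BP" at or above 140/90, and likewise for those with diabetes of 10 years or more. Section 7.4.1 (Enrollment Visit) lists medication history as an element of the visit and says antihypertensive use helps decide "whether renal function testing is recommended prior to initiating medication treatment". Section 2.3 gives the appendices the status of a specification: "The specific protocols and algorithms programmed into this application are described in further detail" there and in the relevant sections.

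**The concern.** Section 7.1 says creatinine would ideally be tested in everyone, and adopts risk-factor triggers because travel to the hospital would deter participation. That substitute works only if the form asks about each trigger in every patient it covers. On the printed routing, the antihypertensive trigger is never asked of a patient new to diabetes drugs. That patient is about to begin metformin, possibly with glibenclamide, which is the moment Section 7.4.1 has in mind.

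At stake is one step in a safety screen. An eGFR below 30 is an exclusion criterion and bars both drugs, and creatinine is the only means the protocol gives to detect it. Section 4.1.3 also counts incorrect application recommendations as a primary safety endpoint. While Appendix 3 and Section 7.1 differ, it is unclear which is the standard for a correct renal-testing recommendation.

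**Working it through.** No arithmetic applies, so the check sets the texts side by side.

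1. **What the phrase means in this list.** The three earlier drug items send a NO to the next question. The past-treatment item sends a NO to the next section. The antihypertensive item also sends both its answers to the next section. Nothing follows it under Medication History, so there the phrase can only mean leaving that section. The ordinary reading of the past-treatment NO branch is therefore an exit that bypasses the antihypertensive item.

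2. **Who is routed this way.** Only patients on no diabetes drug who have never taken one. Current users do not meet the past-treatment item. Past users answer YES, which makes further items appear and is not written as a jump.

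3. **Which of them lose a flag.** Section 7.1 has four triggers:
   - kidney disease history, asked of all in Appendix 1;
   - diabetes duration of 10 years or more, asked of all in Appendix 1;
   - BP at or above 140/90, measured in all at enrollment;
   - antihypertensive use, asked only in Appendix 3.

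   A never-treated patient on antihypertensives who meets any of the first three is still flagged. The one left out has controlled BP, shorter duration and no kidney history.

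4. **Whether that patient starts drug.** Appendix 8 gives an untreated patient no drug at A1c below 6.5 and sends A1c above 14 (or FBG above 400) to consultation. In between, it starts metformin 1700 mg, adding glibenclamide 2.5 mg from A1c 9 to 14. Section 6.5 begins metformin at 850 mg and raises it after 2 weeks.

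5. **What is lost.** Appendix 7 lists renal testing as a routine referral, within 1-2 weeks. Section 2.7.2 requires testing before drug only with a history of kidney disease. Appendix 8 writes no hold on dispensing for patients in whom testing is merely recommended.

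6. **What may recover it.** Appendix 1 asks every enrollee about high blood pressure, and Section 7.4.1 says past medical history helps determine renal testing. However, Appendix 1 attaches no renal trigger to that item, and Section 7.1 does not name self-report. Monthly visits (Section 7.4.2) mirror enrollment except that demographics and medical history are carried forward. If Medication History is repeated, the patient, now on drug, avoids the past-treatment item and reaches the antihypertensive question at about month 1 (+/- 1 week). If it counts as medical history, the omission persists. The text does not settle which.

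7. **After the edit.** If NO leads to the next question, all four triggers are ascertained in every never-treated patient, so every such patient covered by Section 7.1 is flagged.

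**The case against.** The strongest reply is that the wording is loose. The YES branch concerns which side-effect items are displayed, so NO may mean only that they stay hidden. If the next section is the side-effect section, a literal exit sends NO to the very items that YES is meant to reveal. In the side-effect section itself, the same phrase taken literally would skip the aspirin bleeding question, although Section 10.3 says bleeding is asked about at each visit. The bullet nesting is also unreliable in the text available for review. And the main text states the antihypertensive trigger without exception, so a programmer working from it would ask everyone.

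Much of this stands as a reason for caution, and the working application may well behave correctly. It does not remove the conflict. YES reveals items without jumping, so NO can coherently exit to a section whose items stay hidden. Section 10.3 shows a similar conflict at the side-effect item; it does not establish an agreed loose usage. Lost indentation does not change the printed word or the order of the items. That the main text has no exception is the reason the appendix conflicts with it.

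The reply on consequence also has force. A correctly flagged patient might start metformin before the creatinine result, since no hold is written for the recommended group.

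**Conclusion.** The point holds as a minor conflict between Appendix 3 and Sections 7.1 and 7.4.1. It rests on one assumption: that the application follows the printed routing. If so, a never-treated patient on antihypertensives with BP below 140/90, diabetes under 10 years and no kidney disease history misses a recommended routine referral at enrollment, unless the Appendix 1 hypertension answer or a later visit catches it.

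A reader might infer more, and the documents do not support it:

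- **That a mandatory safety test is bypassed.** It is not. The required test depends on kidney disease history, which Appendix 1 asks of everyone.
- **That the flag would have kept drug from a patient with poor renal function.** The text does not show that a flagged patient's drug is held.
- **That the software is faulty.** Only the specification is visible, and it may contain a drafting slip.
- **That the share of affected patients can be gauged by counting trigger combinations.** Such counts weight combinations of unknown frequency equally. The documents do not allow the number of patients to be computed.

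Sample size and the primary analysis are unaffected.

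**What to change.** In Appendix 3, change the destination of the past-treatment NO branch from the next section to the next question. Alternatively, place the antihypertensive question before that branch so every enrollee is asked. For never-treated patients, hide only the side-effect and adherence items. Add this path to the alpha testing already planned in Section 2.7.2.

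The cost is one word in the appendix and, if the application shares the slip, one routing edit. If the application already asks the question, only the text changes. The downside is one extra question per never-treated enrollee and possibly a few more routine referrals, with the travel burden that Section 7.1 describes.
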